- 1) Male or female subjects who are ≥18 years of age, on the day of signing informed consent.
- 2) Have a diagnosis of RA (2010 ACR/EULAR criteria) , and are ACR functional class I-III.
- 3) Have ≥6 swollen joints (from a SJC66) and ≥6 tender joints (from a TJC68) at both Screening and Day 1.
- 4) Must meet at least one of the following parameters at Screening:
 - a) ≥1 documented joint erosion on radiographs of the hands, wrists or feet by central reading AND a positive result for anti-CCP or RF at the central laboratory,
 OR

- b) ≥ 3 documented erosions on radiographs of the hands, wrists or feet by central reading if both antibodies (ie, RF, anti-CCP) are negative (based on central laboratory),
OR
 - c) Serum CRP ≥ 6 mg/L based on central laboratory value
- 5) Ongoing treatment with a stable dose of MTX as described below:
- a) Use of oral MTX on a continuous basis for at least 12 weeks prior to Day 1 and on a stably prescribed dose of 7.5-25 mg/weekly for at least 4 weeks prior to Day 1. Stable doses of <7.5 mg/week are allowed only in the presence of intolerance or toxicity to higher doses or where higher doses are prohibited by the local label or local clinical practice. Doses >25 mg weekly are not permitted during the study.
 - b) Subjects should be receiving an adequate and prescribed stable dose of folic acid (≥ 5 mg/week total dose or as per local clinical practice) which should be confirmed or initiated at Screening, and continued throughout the study.
 - c) Subjects may use concomitant hydroxychloroquine (HCQ) ≤ 400 mg/day or chloroquine ≤ 250 mg/day during the study with the prescription having been stable for at least 4 weeks prior to Day 1.
- 6) Subjects that have failed prior therapy with a bDMARD are not eligible to participate. Subjects with prior exposure to one bDMARD may be enrolled (approximately 20% of total study population) if there is documented evidence of limited exposure (ie, less than 3 months) to the bDMARD .

Study Procedures/
Frequency:

Participating subjects will visit the clinical study center at Screening, Day 1, Weeks 2, 4, 8, 12, 14, 16, 20, 24, 26, 30, 36, 44, and 52 or ET.

For those subjects not entering the LTE, a follow-up visit will be planned 4 weeks after the last dose of study drug (Post Treatment Week 4). Consequently, subjects are planned to be in the study for approximately 60 weeks.

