6.5. Week 52/Early Termination (ET)

If a subject discontinues study, every attempt should be made to perform the required study-related ET and Post-Treatment Week 4 visits and procedures.

Subject's Global Assessment, HAQ-DI and Pain Scale, FACIT-Fatigue, and SF-36, are recommended to be completed before any other study procedures. Invasive study procedures such as blood draws should be done at the end of a study visit.

- Subject's global assessment
- HAQ-DI and Pain Scale
- FACIT-Fatigue and SF-36
- WPAI-RA and EQ-5D, where available
- CCI [REDACTED]
- TSQM, when and where available

- Healthcare resource utilization questionnaire
- Complete Physical examination
- Weight
- Vital signs
- SJC66/TJC68
- Physician's global assessment
- 12-Lead ECG
- Obtain blood samples for:
 - Hematology
 - Serum Chemistry
 - Lipid profile (fasting)
 - Serum CRP
 - Pregnancy test (serum required if subject is entering into LTE)
 - Blood sampling for PK
 - Biomarker blood samples
 - Quantitative Ig at Week 24
 - vfpBMC and leukocyte subsets samples (US and Canada only)
 - CCI
- Urinalysis (including pregnancy test if applicable)
- Urine stored for biomarker analysis Assessment of serious AE(s) (S)AE(s) and concomitant medication
- Radiographs of hands, wrists, and feet
- Carotid artery ultrasound, at selected sites only
- Review Entry criteria for LTE (if applicable)

6.6. Post Treatment Week 4

The following procedures will be completed 4 weeks after the subject's last dose of study treatment. This visit is not applicable if subject is continuing onto the LTE study.

- Symptom-driven physical examination
- Weight
- Vital signs
- 12-lead ECG
- Obtain blood samples for:
 - Hematology and Serum Chemistry
- Urinalysis
- Urine Pregnancy test (females of child bearing potential, as defined per protocol)

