7.2.2. Assessment of Severity

The severity of AEs will be graded using the modified CTCAE, version 4.03. For each episode, the highest grade attained should be reported.

If a CTCAE criterion does not exist, the investigator should use the grade or adjectives: Grade 1 (mild), Grade 2 (moderate), Grade 3 (severe), Grade 4 (life-threatening) or Grade 5 (fatal) to describe the maximum intensity of the adverse event. For purposes of consistency with the CTCAE, these intensity grades are defined in [Table 7-1](#) and [Appendix 4](#).

Table 7-1. Grading of Adverse Event Severity

Grade	Adjective	Description
Grade 1	Mild	Asymptomatic or mild symptoms; clinical or diagnostic observations only; intervention not indicated
Grade 2	Moderate	Local or noninvasive intervention indicated; limiting age-appropriate instrumental ADL
Grade 3	Severe	Severe or medically significant but not immediately life-threatening; hospitalization or prolongation of hospitalization indicated; disabling; limiting self-care ADL
Grade 4	Life-threatening	Urgent intervention indicated
Grade 5	Death	Death related AE

* Activities of Daily Living (ADL) Instrumental ADL refer to opening preparing meals, shopping for groceries or clothes, using the telephone, managing money, etc.

** Self-care ADL refer to bathing, dressing and undressing, feeding self, using the toilet, taking medications, and not bedridden.

7.3. Investigator Requirements and Instructions for Reporting Adverse Events and Serious Adverse Events to Gilead

Requirements for collection prior to study drug initiation:

After informed consent, but prior to initiation of study medication, the following types of events should be reported on the case report form (CRF/eCRF): all SAEs and adverse events related to protocol-mandated procedures.

Adverse Events

Following initiation of study medication, collect all AEs, regardless of cause or relationship, until 30-days after last administration of study drug(s) must be reported to the CRF/eCRF database as instructed.

All AEs should be followed up until resolution or until the adverse event is stable, if possible. Gilead Sciences may request that certain AEs be followed beyond the protocol defined follow up period.

Serious Adverse Events

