8.6. Safety Analysis

All safety analyses will be performed using the safety analysis set.

Safety will be evaluated by assessment of clinical laboratory tests, physical examinations, vital signs measurements at various time points during the study, and by the documentation of AEs.

All safety data collected on or after the first dose of study drug administration up to 30 days after the last dose of study drug, unless specified otherwise, will be summarized by treatment group according to the study drug received.

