Biomarker Blood Samples: Plasma biomarker, serum biomarker, transcriptome, TCR/BCR repertoire ^p		X		X	X	X					X			X		X	
vfPBMC & Leukocyte subsets ^q		X		X	X	X					X			X		X	
Serology ^r	X																
Viral Monitoring ^s						X					X			X		X	
CCI																	

EVENT		Screening ^a	Treatment Period													Follow Up ^d	
			Day 1 ^b	W2	W4	W8	W12	W14	W16	W20	W24	W26	W30	W36	W44	W52/ ET ^c	Post Treatment Week 4
Visits	Visit window (Days)		(±3 days)	(±3 days)	(±3 days)	(±3 days)	(±3 days)	(±3 days)	(±3 days)	(±3 days)	(±3 days)	(±3 days)	(±3 days)	(±7 days)	(±7 days)	(±7 days)	(±7 days)
Imaging	Hand, wrist and feet radiographs ^h	X				X				X					X		
	CCI CCI																
Assessment of Adverse Events		X	X	X	X	X	X	X	X	X	X	X	X	X	X	X	
Concomitant medications		X	X	X	X	X	X	X	X	X	X	X	X	X	X	X	
Randomization/reassignment			X ^x				X ^y			X ^z			X ^{aa}	X ^{aa}	X ^{aa}		
Study Drug(s) Dispensation ^{bb}			X		X	X	X		X	X	X		X	X	X		
Self-injection (or caregiver) training ^{cc}			X														
Review entry criteria for LTE (if applicable)															X		

- a Screening window is 28 days prior to Day 1, the window may be extended to up to 42 days prior to the Day 1 visit for subjects who require repeat collection of radiographs
- b Subject will begin medication on Day 1, following baseline assessments and randomization.
- c Early Termination Visit to be performed if subject discontinues before Week 52
- d The follow-up visit will be performed only for subjects discontinuing prematurely from the study and for those completing Week 52, but not entering the LTE.
- e Eligibility criteria check based on the laboratory results from the Screening visit, TJC/SJC at screening and Day 1 and for female subjects of childbearing potential, the urine pregnancy test at Day 1.
- f Medical History includes smoking status, average weekly alcohol consumption, family history of coronary heart disease (CHD) any other chronic medical conditions or prior surgeries
- g At Screening, Week 24, and Week 52 (or at ET), a complete physical examination should be performed. Symptom-directed exams should be performed at all other visits. Height will be measured at Screening only.
- h Chest X-ray should be performed unless performed in the previous 3 months, and results are available at the site.

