The analysis windows for on-treatment SF-36, FACIT-Fatigue, EQ-5D and WPAI-RA are provided in [Table 3-9](#) and [Table 3-10](#).

Table 3-9. Analysis Visit Windows for On-Treatment SF-36, FACIT-Fatigue, EQ-5D, and WPAI-RA for Subjects who were Initially Randomized to Filgotinib or Adalimumab, and Subjects who were Initially Randomized to Placebo and not Re-randomized

Analysis Visit	Nominal Study Day	Lower Limit	Upper Limit
Baseline	1	(none)	1
Week 4	29	2	57
Week 12	85	58	127
Week 24	169	128	211
Week 36	253	212	309
Week 52	365	310	≥ 365

Table 3-10. Analysis Visit Windows for On-Treatment SF-36, FACIT-Fatigue, EQ-5D, and WPAI-RA for Subjects who were Initially Randomized to Placebo and Re-randomized

Analysis Visit	Nominal Study Day	Lower Limit	Upper Limit
Baseline	1	(none)	1
Week 4	29	2	57
Week 12	85	58	127
Week 24	169	128	First Dose Date of Filgotinib - Study Day 1 + 1
Analysis Visit	On-Filgotinib Study Day	On-Filgotinib Lower Limit	On-Filgotinib Upper Limit
Week 36*	85	2	141
Week 52*	197	142	≥ 197

* For subjects who were on placebo and re-randomized their analysis window after Week 24 will be assigned according to On-Filgotinib Study Day, On-Filgotinib Lower Limit and On-Filgotinib Upper Limit.

Vital signs, weight, ECG, lipids and safety laboratory data collected in the post-treatment follow-up period will also be summarized. The analysis window for the post-treatment follow-up period is defined as from (the last dose date of any study drug + 8 days) to (the last dose date of any study drug + 30 days). If multiple valid, nonmissing measurements exist in the post-treatment follow-up visit window, then the latest record will be selected for analysis. If the chronological order cannot be determined (eg, more than 1 record on the same day with time missing), for any given subject, the value with the worst severity will be selected for categorical variable, and the average will be taken for continuous variable. Data obtained after last dose date plus 30 days will be excluded from the summaries, but will be included in the listings.

For efficacy endpoints, the same analysis visit windows will be applied to all available data collected during standard of care.

3.8.3. Selection of Non-Efficacy Data in the Event of Multiple Records in an Analysis Visit Window

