7.2.2.1. Treatment-Emergent Laboratory Abnormalities

Treatment-emergent laboratory abnormalities are defined as values that increase at least 1 toxicity grade from baseline at any postbaseline time point, up to and including the date of last dose of any study drug plus 30 days for subjects who permanently discontinued study drug, or the last available date in the database snapshot for subjects who were still on treatment at the time of an interim analysis.

For placebo subjects who were then re-randomized, treatment-emergent laboratory abnormalities of placebo period are defined as values that increase at least 1 toxicity grade from the baseline at any postbaseline time point, up to and including the first dose date of filgotinib. Treatment-emergent laboratory abnormalities of re-randomized period are defined as values that increase at least 1 toxicity grade from the new baseline after Week 24 at any postbaseline time point, up to and including the date of last dose of any study drug plus 30 days, or the last available date in the database snapshot for subjects who were still on treatment at the time of an interim analysis.

Placebo subjects who were not re-randomized have treatment-emergent laboratory abnormalities in the placebo period which are defined as values that increase 1 toxicity grade from the baseline at any postbaseline time point, up to and including the date of last dose of any study drug plus 30 days.

If the relevant baseline laboratory value is missing, any abnormality of at least Grade 1 observed within the time frame specified above will be considered treatment emergent.

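### The SAP's post-treatment safety summaries stop at last dose + 30 days, but the protocol lets the Post Treatment Week 4 visit fall as late as day 35

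*SAP*

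**What the plan says.** **Visit timing.** Protocol 6.6 introduces the Post Treatment Week 4 visit with: "The following procedures will be completed 4 weeks after the subject's last dose of study treatment". It lists a symptom-driven examination, weight, vital signs, ECG, hematology and serum chemistry, urinalysis and a pregnancy test. A lipid profile is not listed. The visit-window row of Appendix 2 gives this visit ±7 days.

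**Analysis window.** SAP 3.8.2 covers vital signs, weight, ECG, lipids and safety laboratory data after treatment: "The analysis window for the post-treatment follow-up period is defined as from (the last dose date of any study drug + 8 days") and runs to the last dose date + 30 days. On later values it says: "Data obtained after last dose date plus 30 days will be excluded from the summaries, but will be included in the listings". SAP 7.2 repeats the 30-day limit for laboratory summaries in general, and SAP 7.2.2.1 counts treatment-emergent abnormalities "up to and including the date of last dose of any study drug plus 30 days for subjects who permanently discontinued study drug".

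**Origin of the 30 days.** Protocol 8.6 says that safety data "up to 30 days after the last dose of study drug, unless specified otherwise, will be summarized by treatment group". Protocol 7.3 collects adverse events "until 30-days after last administration of study drug(s".

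**Who has the visit.** Appendix 2 footnote d limits it as follows: "The follow-up visit will be performed only for subjects discontinuing prematurely from the study and for those completing Week 52, but not entering the LTE". The synopsis says that, for those not entering the long-term extension (LTE), "a follow-up visit will be planned 4 weeks after the last dose of study drug (Post Treatment Week 4"). Protocol 6.6 exempts only LTE entrants.

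**The concern.** The post-treatment window in SAP 3.8.2 is where the Post Treatment Week 4 measurements are summarized by group. A visit held exactly as the protocol permits should be usable there. As written, the last five permitted days are not, so a site can comply fully and its data still be left out. At stake is the completeness of the planned group-level view of hematology, chemistry, vital signs, weight and ECG after the drug is stopped.

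A second problem concerns the same visit. Subjects who lose response from Week 30 on, or who stop drug for other reasons, are meant or encouraged to stay in the study (protocol 3.2 and 3.5.2). For them footnote d points to leaving the study or completing Week 52, while 6.6 and the synopsis point to the last dose. When these dates are far apart, the documents do not settle whether an off-drug safety visit takes place near the last dose.

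**Working it through.** **1. Visit window against analysis window**

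Inputs: nominal timing 4 weeks = 28 days (protocol 6.6 and synopsis); tolerance ±7 days (Appendix 2); summary window +8 to +30 days (SAP 3.8.2).

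- Permitted visit days: 28 − 7 = 21 to 28 + 7 = 35, which is 15 days.
- Inside the summary window: days 21 to 30, which is 10 days.
- Outside it: days 31 to 35, which is 5 days; 5/15 = 33%.

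The documents do not say how visits spread within the tolerance, so the share of visits is shown under three assumptions:

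| Assumed spread of visit days | Calculation | Share after day 30 |
|---|---|---|
| Even over days 21–35 | 5/15 | 33% |
| Normal, mean 28, SD 3 | P(Z > (30.5 − 28)/3 = 0.83) | 20% |
| Normal, mean 28, SD 2 | P(Z > (30.5 − 28)/2 = 1.25) | 11% |

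These are shares of the follow-up visits that take place. LTE entrants have none, and the documents give neither LTE-entry nor discontinuation rates for this trial, so no count of subjects follows.

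**2. Subjects who stop drug but stay in the study, if footnote d governs**

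Nominal day = 7 × week + 1 reproduces every post-baseline nominal day in SAP Table 3-1, including Week 30 = 211, Week 36 = 253, Week 44 = 309 and Week 52 = 365. Appendix 2 gives Week 30 ±3 days and Weeks 36, 44 and 52 ±7 days.

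| Last dose at | Next ordinary visit | Nominal gap | Shortest gap within windows |
|---|---|---|---|
| Week 30 | Week 36 | 253 − 211 = 42 days | 42 − 3 − 7 = 32 |
| Week 36 | Week 44 | 309 − 253 = 56 days | 56 − 7 − 7 = 42 |
| Week 44 | Week 52 | 365 − 309 = 56 days | 56 − 7 − 7 = 42 |

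Every gap exceeds 30 days even at its shortest. Loss of response needs two consecutive visits from Week 30 on, so such a stop comes at Week 36 at the earliest; a stop at Week 30 would have another cause.

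For a last dose between visits the picture differs. At nominal timing, of the 99 possible last-dose days from 211 to 309, those with no ordinary visit in the next 30 days are 211–222 (12), 253–278 (26) and 309 (1): 39 in all. The other 60 (223–252 and 279–308) do have one.

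These gaps use the schedule of Appendix 2, the synopsis and SAP Table 3-1. Protocol 6.7.1 lists different late efficacy weeks (32, 36, 40, 48), which would change them.

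**3. Does +35 days solve both?** It covers all 15 permitted follow-up days. It does not reach the next ordinary visit 42 or 56 days later, so the second problem needs its own resolution.

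**The case against.** The strongest reply is that the SAP is faithful to the protocol. Protocol 8.6 sets the 30-day limit, adverse event collection and the treatment-emergent definition stop there too, and values beyond it may reflect standard-of-care therapy rather than study drug. That stands as to origin: a reader might infer that the SAP departs from the protocol, and it does not. The mismatch is between the protocol's visit tolerance and its general summary limit. But 8.6 applies unless specified otherwise, so the SAP may set a longer limit for scheduled measurements.

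Other stronger readings also fail:

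- **The data are lost.** They remain in the listings, the listings of Grade 3 or higher and marked abnormalities carry all results for the test concerned (SAP 7.2.2.3), and all deaths enter the adverse event overview (SAP 7.1.6.1).
- **Lipids are affected.** SAP 3.8.2 names lipids, but this visit collects none.
- **Anyone stopping between Weeks 30 and 44 has no visit within 30 days.** This holds only if footnote d governs, and only for stops at or soon after a visit; 60 of 99 last-dose days have one.
- **A Week 36 stopper would first be followed up 20 weeks off drug.** Footnote d says who has the visit, not when; no passage dates it four weeks after Week 52 for someone who stopped earlier.
- **Subjects stopped for a laboratory criterion contribute nothing.** Protocol 3.5.2 requires retests, 7.6 requires monitoring until values resolve or are explained, and the treatment-emergent rule counts any postbaseline value up to day 30.

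**Conclusion.** The concern holds in a limited form. If the plan is followed exactly, compliant Post Treatment Week 4 visits on 5 of 15 permitted days are left out of the summary meant for them. That is about 11% to 33% of such visits under the assumed spreads, and an unknown number of subjects. No primary or key secondary efficacy analysis is touched, and individual follow-up of abnormal values is unaffected; the loss is in group-level post-treatment summaries. It is worth correcting because the correction is simple and the protocol permits it.

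The conflict between footnote d and protocol 6.6 with the synopsis is real but separate. Its consequence, no ordinary visit within 30 days for a last dose at the Week 30, 36 or 44 visit, depends on footnote d governing and on the Appendix 2 schedule.

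**What to change.** 1. **SAP 3.8.2:** set the upper limit of the post-treatment follow-up window for scheduled laboratory, vital-sign, weight and ECG data to last dose + 35 days, matching the protocol's visit window, and amend the exclusion sentence to agree. SAP 7.2's general 30-day sentence needs a matching exception for this summary. The adverse event and treatment-emergent limits can stay at 30 days.
2. **Protocol:** reconcile Appendix 2 footnote d with 6.6 and the synopsis, so that the documents say one thing about whether and when subjects who permanently stop drug but remain in the study have this visit. Which reading is right is for the sponsor to decide.

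The cost is SAP wording, one date limit in programming and a short protocol clarification; the SAP change adds no subjects or procedures. The small downside is that a few later off-drug values, some possibly obtained under standard of care, enter the post-treatment summary.

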4. SUBJECT DISPOSITION

4.1. Subject Enrollment and Disposition

A summary of subject enrollment will be provided by treatment group for each country within each geographic region and investigator within a country. The summary will present the number and percentage of subjects enrolled. For each column, the denominator for the percentage calculation will be the total number of subjects analyzed for that column.

A similar enrollment table will be provided by stratification factor stratum. The denominator for the percentage of subjects in the stratum will be the total number of enrolled subjects. If there are discrepancies in the value used for stratification assignment between the IWRS and the clinical database, the value collected in the clinical database will be used for the summary. A listing of subjects with discrepancies in the value used for stratification assignment between the IWRS and the clinical database at the time of data finalization will be provided.

The randomization schedule used for the study will be provided in a listing and as an appendix to the CSR.

A summary of subject disposition will be provided by treatment group. This summary will present the number of subjects screened, the number of subjects not randomized, the number of subjects who met all eligibility criteria but were not randomized with reasons subjects were not randomized, the number of subjects randomized, and the number of subjects in each of the categories listed below:

- Safety Analysis Set
- Full Analysis Set
- Per-Protocol Analysis Set
- PK Analysis Set
- PK Substudy Analysis Set
- Continuing study drug (Week 24 Analysis only)
- Completed study drug
- Continuing study (Week 24 Analysis only)
- Did not complete study drug with reasons for premature discontinuation of study drug
- Completed study
- Did not complete study with reasons for premature discontinuation from the study

- Completed Week 24 study drug
- Prematurely discontinued study drug prior to Week 24
- Re-randomized

For the status of study drug and study completion and reasons for premature discontinuation, the number and percentage of subjects in each category will be provided. The denominator for the percentage calculation will be the total number of subjects in the Safety Analysis Set corresponding to that column.

For subjects who were on placebo, they will be considered as completed Week 24 study drug if they were re-randomized. For subjects who were on placebo but were not re-randomized, and subjects who remained on the same treatment, they will be considered as completed Week 24 study drug if $(\text{last dose date} - \text{Study Day } 1 + 1) \geq 156$. Otherwise subjects will be considered as not completed Week 24 study drug.

The following by-subject listings will be provided by subject ID number in ascending order to support the above summary tables:

- Reasons for premature study drug or study discontinuation
- Reasons for screen failure (will be provided by screening ID number in ascending order)
- Lot number and kit ID of assigned study drugs

